### **GOLD Severity of Airflow Limitation Categories**

Table 5: GOLD Severity of Airflow Limitation Categories

GOLD airflow category	Severity	FEV1 threshold
GOLD 1	Mild	≥80% predicted
GOLD 2	Moderate	≥50%, <80% predicted
GOLD 3	Severe	≥30%, <50% predicted
GOLD 4	Very severe	<30% predicted

Note: Based on post-ipratropium values in patients with post-ipratropium FEV1/ FVC <0.70

### **GOLD Categories (2011 Definition)**

Table 6: GOLD Categories

GOLD Category	GOLD Airflow Severity Category	Exacerbations	mMRC
A	GOLD 1-2	≤1	0-1
B	GOLD 1-2	≤1	≥2
C	GOLD 3-4	≥2	0-1
D	GOLD 3-4	≥2	≥2

### **GOLD Categories (2017 Definition)**

Table 7: GOLD Grade

Airflow Limitation	GOLD Grade	Exacerbations	mMRC
>80	1, A	≤1	0-1
	1, B	≤1	≥2
	1, C	≥2	0-1
	1, D	≥2	≥2
50-79.9	2, A	≤1	0-1
	2, B	≤1	≥2
	2, C	≥2	0-1
	2, D	≥2	≥2
30-49.9	3, A	≤1	0-1
	3, B	≤1	≥2
	3, C	≥2	0-1
	3, D	≥2	≥2
<30	4, A	≤1	0-1
	4, B	≤1	≥2
	4, C	≥2	0-1
	4, D	≥2	≥2

Screening data will be used to categorize subjects. For the purposes of categorization, GOLD categories (using 2011 definition to ensure consistency between the efficacy and safety studies in the phase 3 program) will use the GOLD airflow severity category and mMRC scores as the primary method to determine GOLD Category. If GOLD airflow severity is missing, then exacerbations will be used.

In addition, GOLD grade using 2017 definition will also be used for categorizing the subjects.

### **8.2 Efficacy Variables**

[REDACTED]

[REDACTED] his analysis plan where the weighted mean (WM) is the AUC/total time, nominally, 4 H.

[REDACTED]

[REDACTED]

[REDACTED]

[REDACTED]

[REDACTED]

[REDACTED]

[REDACTED]

[REDACTED]

### 8.3 Safety Variables

#### Adverse Events

Adverse events (AEs) are recorded from signing of the informed consent form through the final follow-up assessment. Non-treatment-emergent AEs and treatment-emergent AEs (defined in Section 9.3.2) will be summarized separately.

#### Bronchodilators by Drug Class

Appendix 2 contains coding logic for determination of specific drug classes for bronchodilators.

## 9 ANALYSES

Table, figures and listing titles are denoted in underlined text.

## 9.1 General Analyses

### 9.1.1 Subject Disposition

Subject disposition information will be summarized for all subjects by treatment group.

Summaries will include the following parameters:

- Number of randomized subjects,
- Number and percentage of subjects randomized and treated with study drug (ITT Analysis set),
- Number of subjects randomized, but not dosed
- Number and percentage of subjects completing the study,
- Number and percentage of subjects by reason discontinuing the study drug,
- Number and percentage of subjects by reason discontinuing the study.

A listing of subject disposition will include the ITT analysis set status, the date of informed consent signed, the date of first dose and last dose of study drug, primary reason for subject discontinuation of study medication, the date of last visit, study completion status, primary reason for study termination, and the date of last contact.

### 9.1.2 Demographics and Baseline Characteristics

Demographics and baseline characteristics (age, sex, race, ethnicity, height, weight, and BMI) will be summarized for ITT set.

A listing of demographics and baseline characteristics will also be provided.

### 9.1.3 Reversibility Summaries

A post-bronchodilator screening reversibility summary taken during screening visits will be provided with the following parameters:

- Ipratropium reversibility (mL),
- Ipratropium reversibility (%),

In addition, a post-bronchodilator screening reversibility categorical summary will be provided in a separate summary:

- Not reversible to ipratropium,
- Reversible to ipratropium,

Separate listings will also be provided. The ITT analysis set will be used for the summaries.

#### **9.1.4 Screening and Baseline Spirometry Summaries**

A screening spirometry summary will be provided with the following parameters:

- Post-ipratropium predicted Normal FEV1 (mL),
- Post-ipratropium percent predicted FEV1 (%),
- Post-ipratropium FEV1 (mL),
- Post-ipratropium FVC (mL),
- Post-ipratropium FEV1 to FVC (ratio),

A Baseline spirometry summary will be provided in a separate table with the following parameters:

- Baseline FEV1 (mL)
- Baseline FVC (mL)
- Baseline PIFR (L/min)
- Baseline PIFR by Category ( $\leq 40$ ,  $> 40$ )
- Baseline IC (L)
- Baseline MIP (cm H2O)
- Baseline FEV1 to FVC (ratio)
- Baseline predicted Normal FEV1 (mL)
- Baseline percent predicted FEV1 (mL)

A single listing that includes screening, baseline and post-baseline spirometry will be provided. The ITT analysis set will be used for the summaries.

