## 8 DEFINITION OF ANALYSIS VARIABLES

### 8.1 General Variables

#### Age

Age will be calculated as of the date of signing informed consent and truncated to its integer value. The following formula is used:

$$\text{Baseline Age} = \text{floor} \left( \frac{\text{Date of Informed Consent} - \text{Date of Birth}}{365.25} \right).$$

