### 9.1.5 Baseline Clinical Characteristics Summaries

A summary of COPD clinical characteristics taken at baseline will be provided with the following parameters:

- Proportion of subject with baseline PIFR  $\geq 40$  L/min
- Proportion of subject  $\geq 65$  years of age (%),
- Duration of COPD (years),
- Proportion of subjects with a history of supplemental oxygen use (%),

A summary of smoking characteristics taken at baseline will be provided with the following parameters:

- Smoking history, current and former, (%),
- Number of years smoked (years),
- Maximum number of packs per day (packs),
- Pack years (packs).

A summary of LABA and ICS use will be provided with the following parameters using coded concomitant medication data:

- Concurrent ICS use (%),
- Concurrent LABA use (%),
- Subgroup: Concurrent QD LABA use (%),
- Subgroup: Concurrent BID LABA use (%),
- Concurrent ICS/LABA use (%).

Three listings will also be provided. The ITT analysis set will be used for the summaries.

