### 9.1.7 Key Demographic and Baseline Characteristics Summary

A summary of key demographic and baseline characteristics will include the following with the following parameters on a single page:

- Age, mean(SD),
- Sex (male), %,
- Race (white), %,
- BMI, mean (SD),
- Current smoker (yes), %,
- Concurrent ICS use (yes), %,
- Concurrent LABA use (yes), %,
- Concurrent ICS/LABA use (yes), %,
- Post-ipratropium percent predicted FEV1, mean (SD),
- Post-ipratropium FEV1 to FVC (ratio), mean (SD),
- Baseline FEV1 (in mL), mean (SD),
- Baseline FVC , mean (SD),
- Baseline IC, mean(SD)
- Baseline PIFR (L/min), mean (SD),
- Baseline PIFR ( $\geq 40$  L/min), %
- Baseline MIP (cm H2O), mean (SD)
- Baseline MIP, mean (SD)
- Proportion of subjects with baseline mMRC  $\geq 2$ , %
- Proportion of subjects with  $\leq 1$  exacerbations in prior year, %
- BDI score, LS mean (SE)

For continuous summaries, only the “mean (SD)” will be displayed. As this data is summarized in listing format elsewhere, no listing is provided for this summary. The ITT analysis set will be used for the summary.

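### Do the differing boundary signs at a PIFR of 40 L/min and at age 65 require a change to the SAP?

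*SAP*

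**What the plan says.** Four sections of the SAP use a cut at 40 L/min for baseline PIFR or at 65 years for age.

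- **PIFR, section 9.1.4** (baseline spirometry table): "Baseline PIFR by Category ( $\leq 40$ , $> 40". A value of 40 is low.
- **PIFR, section 9.1.5** (clinical characteristics table): "Proportion of subject with baseline PIFR $\geq 40$ L/min". A value of 40 is high.
- **PIFR, section 9.1.7** (one-page key baseline table): "Baseline PIFR ( $\geq 40$ L/min". A value of 40 is high.
- **Age, section 5.1** (list of general endpoints): two categories, 65 and under against over 65. Age 65 is in the younger one.
- **Age, section 9.1.5**: "Proportion of subject $\geq 65$ years of age". Age 65 is in the older group.

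Section 8.1 defines age as completed years, "truncated to its integer value". Sections 9.1.4, 9.1.5 and 9.1.7 all use the ITT set. Section 7.4.1 names baseline PIFR and age among the pre-defined subgroups, but their cut points are redacted.

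**The concern.** The same cut points carry different signs, so a subject exactly on the boundary is in one group in one table and in the other group elsewhere. The usual innocent explanations do not remove this. The analysis set is the same in the three tables. Table 2 gives PIFR a single baseline visit (Visit 1B). No legible text links one form of the 40 L/min cut to one of the two device resistances mentioned in section 3.

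PIFR also matters in this trial. Suboptimal PIFR is an entry condition, and baseline PIFR is the first subgroup listed in section 7.4.1. If the ambiguity reached the subgroup analysis, two programmers could form different low-PIFR groups, and the side given to the boundary value could be settled after results were known. Even without that, one report could show PIFR percentages on the same denominator that do not agree.

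**Working it through.** **Applying each written rule around the boundary**

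| Value | Section 9.1.4 | Sections 9.1.5 and 9.1.7 |
|---|---|---|
| PIFR 39.9 | ≤40 | not ≥40 |
| PIFR 40 | ≤40 | ≥40 |
| PIFR 40.1 | >40 | ≥40 |

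| Exact age | Age as derived (8.1) | Section 5.1 | Section 9.1.5 |
|---|---|---|---|
| 64.99 | 64 | ≤65 | not ≥65 |
| 65.00 | 65 | ≤65 | ≥65 |
| 65.99 | 65 | ≤65 | ≥65 |
| 66.00 | 66 | >65 | ≥65 |

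Only a PIFR of exactly 40 changes side. For age, the whole year from 65.00 to 65.99 changes side because age is truncated.

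**Size of the disagreement.** Let k be the number of subjects at the boundary, b the number above it and N the number tabulated. The percentage above the cut is 100 × b/N. The percentage at or above it is 100 × (b + k)/N. The difference is 100 × k/N. With N = 200 (SAP section 4, about 100 per group), taking all randomized subjects as tabulated:

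| k | Difference, all 200 | Difference in one arm of 100 if all k are in it |
|---|---|---|
| 0 | 0 points | 0 points |
| 1 | 0.5 | 1 |
| 5 | 2.5 | 5 |
| 10 | 5.0 | 10 |
| 20 | 10.0 | 20 |

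**What k might be.** The SAP gives neither the recording step of PIFR nor the spread of PIFR or age, so these are assumptions.

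- PIFR in 1 L/min steps, even over 20 to 59: 200 × 1/40 = 5 subjects, or 2.5 points.
- PIFR in 5 L/min steps, even over 20 to 55: 200 × 1/8 = 25 subjects, or 12.5 points.
- Age normal with mean 63 to 67 and SD 7 to 9: 200 × P(65 ≤ age < 66) = 8.5 to 11.4 subjects, or about 4.3 to 5.7 points.

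The PIFR figures are soft. They need an even spread and they assume that the tabulated PIFR lies below 60 L/min. Section 3 applies that limit at the inclusion resistance only. PIFR is measured at two resistances, and Table 2 does not visibly say which one supplies the baseline. For PIFR, k = 0 cannot be excluded. For age, some subjects at 65 are likely.

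**Where the cuts are used.** The legible uses are the endpoint list in section 5.1 and rows of baseline tables in sections 9.1.4, 9.1.5 and 9.1.7. The primary hypothesis in section 9.2.2 compares mean change in trough FEV1 between treatments and uses neither cut. Eligibility uses 60 L/min, a different threshold.

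**The case for a change.** The strongest case for acting is that the contradiction is verified in current, unredacted text, concerns a variable central to the trial, and would cost a few words to remove before unblinding. A pre-specified plan should fix its boundaries, and someone following it literally has to derive two PIFR flags and two age flags. All of that is fair, and the mismatch itself stands.

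The step from there to harm does not stand. The subgroup cuts in section 7.4.1 are blacked out, so nothing shows that they are 40 or 65, that they are ambiguous, or that they conflict with the baseline tables. The section describes the subgroups as pre-defined, so a choice of boundary after unblinding is conjecture. In the baseline tables there is no choice to make, since every row states its own sign. A row for values above 40 and a row for values at or above 40 can both be correct and correctly labelled, and the gap between them is the count at the boundary. The cut points themselves agree; only the treatment of equality differs.

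**Conclusion.** No change to the plan follows. This is a clerical inconsistency in descriptive baseline summaries. As written, the plan yields accurate, correctly labelled percentages that may differ by 0.5 points overall for each boundary subject among 200. For age the gap is plausibly around 4 to 6 points under the assumed age spread. For PIFR it may be anything from zero to the 12.5 points of the least favourable assumed case. No hypothesis test, treatment estimate, eligibility decision or conclusion is shown to move.

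A statistician preparing the table shells, which section 6.6 places in a separate document, would ordinarily settle on one sign for each variable and check it against the subgroup definitions. That is routine housekeeping.

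The conclusion rests on the legible text. It assumes that the redacted subgroup definitions each state a single rule and that the redacted model text does not use these two cuts. Neither can be checked here, and redacted text is no evidence of a fault.

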### 9.1.5 Baseline Clinical Characteristics Summaries

A summary of COPD clinical characteristics taken at baseline will be provided with the following parameters:

- Proportion of subject with baseline PIFR  $\geq 40$  L/min
- Proportion of subject  $\geq 65$  years of age (%),
- Duration of COPD (years),
- Proportion of subjects with a history of supplemental oxygen use (%),

A summary of smoking characteristics taken at baseline will be provided with the following parameters:

- Smoking history, current and former, (%),
- Number of years smoked (years),
- Maximum number of packs per day (packs),
- Pack years (packs).

A summary of LABA and ICS use will be provided with the following parameters using coded concomitant medication data:

- Concurrent ICS use (%),
- Concurrent LABA use (%),
- Subgroup: Concurrent QD LABA use (%),
- Subgroup: Concurrent BID LABA use (%),
- Concurrent ICS/LABA use (%).

Three listings will also be provided. The ITT analysis set will be used for the summaries.

### 9.1.6 GOLD Category Summary

A summary of GOLD categories will be provided with the following parameters:

- GOLD Severity of Airflow Limitation groups,
- 2011 GOLD Categories,
- 2017 GOLD Categories

A listing will be provided. The ITT analysis set will be used for the summary.

### 9.1.7 Key Demographic and Baseline Characteristics Summary

A summary of key demographic and baseline characteristics will include the following with the following parameters on a single page:

- Age, mean(SD),
- Sex (male), %,
- Race (white), %,
- BMI, mean (SD),
- Current smoker (yes), %,
- Concurrent ICS use (yes), %,
- Concurrent LABA use (yes), %,
- Concurrent ICS/LABA use (yes), %,
- Post-ipratropium percent predicted FEV1, mean (SD),
- Post-ipratropium FEV1 to FVC (ratio), mean (SD),
- Baseline FEV1 (in mL), mean (SD),
- Baseline FVC , mean (SD),
- Baseline IC, mean(SD)
- Baseline PIFR (L/min), mean (SD),
- Baseline PIFR ( $\geq 40$  L/min), %
- Baseline MIP (cm H2O), mean (SD)
- Baseline MIP, mean (SD)
- Proportion of subjects with baseline mMRC  $\geq 2$ , %
- Proportion of subjects with  $\leq 1$  exacerbations in prior year, %
- BDI score, LS mean (SE)

For continuous summaries, only the “mean (SD)” will be displayed. As this data is summarized in listing format elsewhere, no listing is provided for this summary. The ITT analysis set will be used for the summary.

## 9.2 Efficacy Analysis

### 9.2.1 General Considerations for Efficacy Analyses

#### Analysis Set for Efficacy Analyses

For all efficacy data analyses, the ITT analyses set will be used unless otherwise specified.

### 9.2.2 Primary Efficacy Evaluation: Trough FEV1

#### Hypothesis

The null hypothesis will be that there is no difference between revefenacin (175 mcg) and tiotropium (18 µg) in change from baseline trough FEV1 on Day 29.

Symbolically, this is expressed as follows:

$$H_0: \mu_{REV} = \mu_{TIO}$$

[figure not shown]
$$H_1: \mu_{REV} \neq \mu_{TIO}$$

#### Analysis and Summary Tables

## Figures

### **9.2.3 Secondary Efficacy Evaluation: Trough FVC and Trough IC**

#### Hypothesis

The null hypothesis will be that there is no difference between revefenacin (175 mcg) and tiotropium (18  $\mu$ g) in change from baseline trough FVC and trough IC on Day 29, respectively.

Symbolically, this is expressed as follows:

$$H_0: \mu_{REV} = \mu_{TIO}$$

$$H_1: \mu_{REV} \neq \mu_{TIO}$$

## **Analysis and Summary Tables**

Similar approach used for the primary efficacy endpoint of change from baseline trough FEV1 will apply for Trough FVC and trough IC, respectively.

Similar code used for primary analysis will be used for trough FVC and trough IC.

Topic	Percentage
Smart homes	98
Smart cities	97
Smart grids	96
Smart transportation	95
Smart agriculture	94
The concept of a 'smart city'	60
Smart energy storage	92
Smart waste management	93
Smart water management	90
Smart manufacturing	88
Smart healthcare	85
Smart education	82
Smart retail	78
Smart government services	75
Smart leisure and tourism	72
Smart sports and fitness	68
Smart fashion and apparel	65
Smart food and beverage	62
Smart automotive	58
Smart consumer products	55
Smart home security	52
Smart wearables	48
Smart medical devices	45
Smart sensors	42
Smart connectivity	38
Smart data analysis	35
Smart robotics	32
Smart materials	28
Smart manufacturing processes	25
Smart supply chain management	22
Smart logistics	18
Smart energy infrastructure	15
Smart waste reduction	12
Smart water conservation	10
Smart energy efficiency	8
Smart resource management	5
Smart environmental monitoring	3
Smart waste recycling	2
Smart energy storage technologies	1
Smart energy generation	0

#### 9.2.4 Secondary Efficacy Evaluation: Peak FEV1 and Peak FVC (0-4 hours)

## Hypothesis

The null hypothesis will be that there is no difference between rerefenacin (175 mcg) and tiotropium (18 µg) in change from Baseline peak FEV1 and peak FVC on Day 1 and Day 29.

## **Analysis and Summary Tables**

A series of horizontal black bars of varying lengths, likely representing data points or categories in a visualization. The bars are arranged in a grid-like pattern, with some rows containing multiple bars and others containing a single bar. The lengths of the bars vary significantly, with some being very short and others being very long. The bars are set against a white background and are rendered in a solid black color.

**Figures**

[REDACTED]

[figure not shown]
**9.2.6 Exploratory Efficacy Evaluation: [REDACTED]**

[REDACTED]

#### 9.2.7 Exploratory Efficacy Evaluation: [REDACTED]

A summary of TDI Responders ( $\geq 1$  units) will include observed counts and proportions (using frequency reporting format) and observed least-square proportions and odd ratios on the differences between treatment groups (using BLS MEAN format). Nominal p values and multiplicity adjusted p values will be reported.

#### 9.2.8 Exploratory Efficacy Evaluation: [REDACTED]

### 9.3 Safety Analyses

For all safety analyses, the safety analysis population will be used.

Safety variables to be summarized include exposures, concomitant medication, vital signs and adverse events. Vital signs will be summarized in terms of observed values and changes from baseline.

### **9.3.1 Extent of Exposure**

Study drug exposure (Number of Doses and Days) will be summarized using the eight-point descriptive summary by study periods. The source for exposure data is the drug accountability data domain.

Study drug compliance will be assessed using the following categories using the same source as the drug exposure data by study periods:

- 100%;
- 95%;
- 90%;
- 80%;
- <80%.

Study drug administration (date/time and study day) will be provided in a data listing. The source for study drug administration is the diary data domain.

### **9.3.2 Adverse Events**

Adverse events will be coded to the preferred terms of the Medical Dictionary for Regulatory Activities (MedDRA®). Summaries will present by system organ class (SOC), preferred term (PT) and severity and/or relatedness, the frequency and percentage of subjects reporting each observed event.

A treatment-emergent adverse event (TEAE) will be defined as any AE that begins on or after the date of first dose of study drug up to the date of last dose of study drug plus 7 days in the follow-up period. AEs observed during the period from obtaining informed consent to the start of administration of study drug will be regarded separately from TEAEs. Treatment-limiting AEs are defined as any event that leads to permanent or temporary discontinuation from treatment.

Summary of adverse events will be dependent on adverse events observed. If no adverse events meeting a specific table are observed, the summary table will not be completed.

Blank summary tables will not be utilized. The following is the list of adverse event tables:

Overall:

- Overall Summary of Adverse Events

By preferred term:

- Treatment-emergent Adverse Events by SOC and PT
- Treatment-emergent Adverse Events by PT
- Treatment-emergent Adverse Events by SOC and PT occurring in more than 1% of Study population
- Treatment-emergent Adverse Events by SOC, PT and LABA Use

By severity:

- Treatment-emergent Adverse Events by SOC, PT and Severity
- Moderate or Severe Treatment-emergent Adverse Events by SOC and PT
- Serious Adverse Events
- Deaths during Study

By relatedness:

- Drug-Related Treatment-emergent Adverse Events by SOC and PT
- Drug-Related Treatment-emergent Adverse Events by SOC, PT and LABA Use
- Drug-Related Treatment-emergent Adverse Events by SOC, PT and Severity
- Moderate or Severe Drug-Related Treatment-emergent Adverse Events by SOC and PT
- Drug-related Serious Adverse Events

Other:

- Adverse Events Leading to Premature Study Drug Discontinuation
- Adverse Events Leading to Temporary Interruption of Study Drug

The overall summary of adverse events will include the following summary lines, any AE, moderate or severe AEs, moderate or severe AEs related to Study Drug, serious AEs, serious AEs related to Study Drug, AEs leading to discontinuation, AEs leading to interruption, deaths during Study.

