### **Safety Endpoints**

The following windows summarize the definition of treatment-emergent.

Table 4: Analysis Windows: Treatment Emergent Events

Window	Start	Stop
Adverse events	Signing of ICF	Maximum of Follow-up visit or Last dose + 7 days
Treatment-emergent Adverse events	Post first dose	Last dose + 7 days

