### 9.3.2.1 Antimuscarinic Adverse Events

Antimuscarinic TEAEs are of interest as a common event in the drug class and will be summarized by preferred terms. The preferred terms for TEAEs considered antimuscarinic are as follows:

- Constipation
- Dry mouth
- Dysuria
- Worsening of urinary retention
- Worsening of narrow-angle glaucoma.

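### An adverse event open at first dose that worsens on treatment is not counted as treatment-emergent if it stays on its original record

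*SAP*

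**What the plan says.** Section 9.3.2 defines a TEAE as "any AE that begins on or after the date of first dose of study drug up to the date of last dose". The window closes a week after the final dose: "up to the date of last dose of study drug plus 7 days in the follow-up period". The next sentence deals with earlier events: "AEs observed during the period from obtaining informed consent to the start of administration of study drug will be regarded separately from TEAEs".

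Section 8.3 names Section 9.3.2 as the governing definition and keeps the two classes apart: "Non-treatment-emergent AEs and treatment-emergent AEs (defined in Section 9.3.2) will be summarized separately". It also fixes the collection period: "Adverse events (AEs) are recorded from signing of the informed consent form through the final follow-up assessment".

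Table 4 in Section 6.1.2 is introduced with "The following windows summarize the definition of treatment-emergent". Its TEAE row starts at "Post first dose" and stops at last dose plus 7 days. It is a time window and nothing more.

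The adverse event rules under missing data (Section 6.1.3) cover a missing grade and a missing causality assessment. They do not address a change in severity. Section 9.3.2.1 lists five antimuscarinic TEAE terms, two of which describe worsening of a condition, for example "Worsening of urinary retention".

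**The concern.** Collection begins at consent, so an adverse event can be open when the first dose is given. The classification uses the start date alone. Nothing in the visible text brings in an event that began before dosing and then became more severe, or became serious, on treatment.

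Aggravation on treatment is something TEAE tables are expected to show. Here two antimuscarinic drugs are compared, and the severity, drug-related and antimuscarinic tables are where a reader would look for it. If such events are classed with the pre-treatment events, those tables miss them in whichever arm they occur. The primary endpoint and its test are not affected.

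**Working it through.** The SAP states no figure on this point, so the check is a trace of the rule, followed by a short illustration of size.

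**Trace.** Take dry mouth, which is on the antimuscarinic list. It is reported as mild after consent and before the Day 1 dose, is still ongoing at Day 1, and becomes severe on Day 10. Suppose it stays on one record.

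1. Recorded as an adverse event? Yes. Section 8.3 and Table 4 both start collection at consent.
2. Starts on or after the first-dose date? No. It fails the test in Section 9.3.2.
3. Is there an exception for later worsening? No. The sentence on pre-dose events has none, Table 4 adds none, and Section 6.1.3 has no rule on change in severity.
4. Result: non-treatment-emergent, although its severe phase lies wholly inside the treatment window.

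**Where the event then appears.**

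| Output in Section 9.3.2 or 9.3.2.1 | Restricted to TEAEs by title or text? | Event shown? |
|---|---|---|
| By SOC and PT; by PT; above 1%; by LABA use | Yes | No |
| By severity; moderate or severe | Yes | No |
| Drug-related TEAE tables | Yes | No, even if judged related |
| Antimuscarinic summary | Yes | No, though the term is listed |
| Overall summary | No | Possible |
| Serious events, drug-related serious events, deaths | No | Possible, if it qualifies |
| Leading to discontinuation or interruption | No | Possible, if it qualifies |

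Section 8.3 also provides for a separate summary of non-treatment-emergent events. The event would be counted there, but under a heading that does not mark it as on-treatment worsening.

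**The same course recorded differently.** If the worsening is entered as a new record with onset on Day 10, that record passes the start-date test and is a TEAE under the present wording. The classification therefore turns on a recording convention that the SAP does not state.

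**Size, on assumption only.** The SAP plans about 200 randomized subjects (Section 4) and gives no count of screening events. Suppose 5% to 10% of subjects have an event open at first dose and 10% to 20% of those worsen on the same record. Neither range comes from the SAP.

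- Low: 200 × 0.05 × 0.10 = 1 subject.
- High: 200 × 0.10 × 0.20 = 4 subjects, across both arms and all terms.

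**Sensitivity of the 1% table.** With 200 subjects, more than 1% means more than 2, so at least 3. One omitted subject removes a term that would otherwise have had exactly 3. This matters only for a term sitting at that threshold.

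**The case against.** The strongest objection is that the omission depends on how worsening is recorded, which is commonly left to the protocol or the eCRF instructions. If a new record is opened when severity increases, the definition works as written. This stands, and the point is conditional on it. It does not remove the point, because the SAP chose to define a TEAE, Section 8.3 relies on that definition, and the SAP neither states nor cites such a convention.

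A reader might infer that the antimuscarinic list contradicts the definition, since two of its terms describe worsening. The documents do not support that. These terms fit aggravation of a condition already in the medical history, reported as a new adverse event with onset on treatment, and such an event passes the start-date test. If anything, the list hints that worsening may be recorded as its own event.

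A reader might also infer that common COPD symptoms such as dyspnoea or cough are widely affected. Symptoms that predate consent would ordinarily be medical history, which is collected at screening, and not open adverse events. The gap is confined to events that began between consent and first dose, were still ongoing, and worsened on the same record.

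Finally, a reader might infer that these events vanish from reporting or that every TEAE table is understated. Neither follows. Several key tables are not restricted to TEAEs, and a drug-related or antimuscarinic table changes only if the event in question qualifies for it.

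**Conclusion.** The point holds in conditional form. As written, Section 9.3.2 and Table 4 classify by start date alone. An event open at first dose that worsens on its original record is left out of the TEAE-restricted tables for which it would otherwise qualify. It may still appear in the overall, serious, death, discontinuation and interruption tables, and in the non-treatment-emergent summary.

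The number affected is likely small and cannot be computed from the SAP; the 1 to 4 subjects rest wholly on the assumed ranges. The conclusion assumes that no convention outside the SAP opens a new record on worsening. It is worth correcting because the rule is explicit, it bears on the safety comparison of the two arms, and the change is cheap.

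**What to change.** In Section 9.3.2 and in the TEAE row of Table 4, define a TEAE as an adverse event that begins after first dose and up to last dose plus 7 days, or that began before first dose and increases in severity or becomes serious within that window. Amend the sentence on pre-dose events so that those which later worsen in this way are not set apart.

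Also state how worsening is recorded:

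- If the eCRF opens a new record on worsening, say that the onset rule applies to that record.
- If it stores only one maximum severity per event, confirm before programming that the timing of worsening can be derived.

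While editing, align the two start points: Section 9.3.2 works from the date of first dose, whereas Table 4 starts after the dose, so an event on Day 1 before dosing is classified differently.

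The cost is a few lines of SAP text and a small amount of programming. The downside is slightly higher reported TEAE counts.
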